2.7.2 Adverse events (AEs)

AEs will be graded by the investigator according to the NCI-CTCAE, Version 4.03. Adverse events will be coded to the PT level using Medical Dictionary for Regulatory Activities (MedDRA).

The following adverse event summaries will be produced by treatment group: overview of adverse events and deaths (number and % of subjects who died, any AE, any SAE, any dose reductions/interruptions, AEs related to study treatment, SAEs related to study treatment, AEs leading to treatment discontinuation, AEs requiring additional therapy, AEs leading to withdrawal), AEs by SOC and PT summarized by relationship (all AEs and AEs related to study treatment), SAEs by SOC and PT.

A summary of all AEs that occurred in strictly 5% or higher of all the subjects will be provided (no rounding for the percentage will be used in terms of 5% threshold, e.g., event with 4.9% incidence rate should not be included in this table). The summary will be displayed by preferred term (PT) and maximum grade.

The summary will use the following algorithms for counting the subject:

- **Preferred term row:** Subjects experiencing the same AE preferred term several times with different grades will only be counted once with the maximum grade.
- **Any event row:** Each subject with at least one adverse event will be counted only once at the maximum grade no matter how many events they have.

These summaries are displayed in descending order of Octreotide+Lap+Cap group by SOC and PT. In the SOC row, the number of subjects with multiple events under the same system organ class will be counted once.

A study treatment-related AE is defined as an AE for which the investigator classifies the relationship to study treatment as “Yes”. A worst case scenario approach will be taken to handle missing relatedness data, i.e., the summary table will include events with the relationship to study treatment as ‘Yes’ or missing. The summary table will be displayed in descending order of Octreotide+Lap+Cap group by SOC and PT

A listing for all AEs will be provided including seriousness, relatedness, action taken.

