**9.3.5.2.2. Adverse events**

Adverse events (AEs) will be coded using the standard GSK Medical Dictionary for Regulatory Activities (MedDRA) and grouped by system organ class. AEs will be graded by the investigator according to the NCI-CTCAE (version 4.03).

The AE terms diarrhoea and frequent bowel movements will be aggregated to form the term diarrhoea in accordance with the Aggregation Guidelines for AE Terms in Lapatinib Studies.

The number and percentage of subjects experiencing adverse events will be summarised by system organ class and preferred term. Separate summaries will be given for all AEs, drug-related AEs, SAEs and AEs leading to discontinuation of study treatment.

If the AE is listed in the NCI CTCAE (version 4.03) table, the maximum grade will be summarised.

Characteristics (e.g. number of occurrences, action taken, grade and severity) of the following AEs of special interest will be summarised separately: diarrhoea, rash, nausea, vomiting, hepatobiliary events, cardiac events, and pneumonitis.

The incidence of deaths and the primary cause of death will be summarised.

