2.8	Health outcomes analyses	32
2.8.1	Health Outcomes Assessments.....	32
2.9	Interim analysis	33
3	Sample size calculation.....	33
3.1	Sample size assumptions.....	33
3.2	Sample Size Sensitivity.....	33
3.3	Sample Size Re-estimation	34
4	Change to protocol specified analyses.....	34
5	Appendix.....	34
5.1	Imputation rules	34
5.1.1	AE date imputation.....	35
5.1.2	Concomitant medication and blood and blood supportive care products	36
5.1.3	Other imputations	38
5.2	AEs coding/grading.....	38
5.3	Statistical models	39
5.3.1	Analysis of binary data.....	39
5.3.2	Analysis of time to events data.....	40
6	Reference	40

List of abbreviations

AE	Adverse event
ATC	Anatomical Therapeutic Classification
CSR	Clinical Study report
CTC	Common Toxicity Criteria
CTCAE	Common Terminology Criteria for Adverse Events
DMC	Data Monitoring Committee
DMD	Diarrhoea Management Diary
eCRF	Electronic Case Report Form
FACIT-D	Functional Assessment of Chronic Illness therapy-Diarrhoea
FACT-G	Functional Assessment of Cancer Therapy-General
MedDRA	Medical Dictionary for Drug Regulatory Affairs
NCI	National Cancer Institute
PRO	Patient-reported Outcomes
RECIST	Response Evaluation Criteria in Solid Tumors
SAP	Statistical Analysis Plan
SOC	System Organ Class

1. Introduction

This statistical analysis plan (SAP) describes analyses required for a Clinical Study Report (CSR) to support a publication of study LAP016A2410, a randomised, multicentre, open label, phase II study of Prophylactic Octreotide to prevent or reduce the frequency and severity of diarrhoea in subjects receiving Lapatinib with Capecitabine for the treatment of metastatic breast cancer. This is a phase II study to evaluate the efficacy, safety [REDACTED] of prophylactic octreotide compared to no octreotide using a parallel group, open label, randomised study design.

As first interim analysis results showed study is futile and no patients will be recruited in the study. For final analysis abbreviated CSR will be done and it will include reduced analyses as compared to planned analyses in the protocol.

As planned in the protocol an interim analysis was performed after 62 patients enrolled using a cut-off date (30-Mar-2016) and an interim database lock on 16-Aug-2016. As the interim analysis results showed study was futile the DMC recommended to stop the study. Per protocol no further patients were enrolled in the study per IA cut-off.

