1.1 Study design

This is a randomised, parallel group, multi-centre, open-label Phase II study in subjects with HER2-positive metastatic breast cancer which has progressed following prior therapy, which must have included anthracyclines and taxanes and therapy with trastuzumab in the metastatic setting. This study is not placebo controlled, and there is no active comparator.

Subjects must be screened for eligibility and informed consent must be given before any study-related procedures are conducted.

All subjects will receive treatment with lapatinib 1250mg once daily and capecitabine 1000mg/m² twice daily until disease progression. Lapatinib will be given every day; capecitabine will be given in 3 week cycles of two weeks treatment followed by one week off treatment. All subjects with episodes of diarrhoea will be encouraged to follow the diarrhoea management guidelines for subjects receiving lapatinib. One cycle of lapatinib and capecitabine equates to three study weeks.

Subjects will be randomised in a 1:1 ratio to receive either:

- Octreotide (Sandostatin long acting release (LAR)) 40mg 7 days before the start of treatment with lapatinib and capecitabine and again 28 days later, or

- No octreotide treatment.

For subjects randomised to receive octreotide, treatment with lapatinib and capecitabine will be initiated 7 days after the first dose of octreotide given as the LAR formulation. For subjects randomised to receive no octreotide, treatment with lapatinib and capecitabine will be initiated immediately following enrolment.

Subjects randomised to receive octreotide LAR must be given one 0.1mg dose of the standard formulation of octreotide subcutaneous (s.c.) to assess tolerability at least one hour before the first dose of the LAR formulation is administered. Subjects with significant intolerance to octreotide 0.1mg s.c. will not receive treatment with octreotide LAR, but will receive treatment with lapatinib and capecitabine as scheduled.

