2.2 Analysis Populations

Intent-to-Treat Population

The Intent-to-Treat (ITT) population will comprise all randomised subjects regardless of whether or not treatment was administered. This population will be based on the treatment to which the subject was randomised. Any subject who receives a treatment randomization number will be considered to have been randomised. The primary analysis of disease efficacy and all diarrhoea-related efficacy endpoints will be analysed using the ITT population.

Modified ITT

The modified ITT (m-ITT) population will comprise all subjects in the ITT population and under Octreotide arm this population will include subjects who do not show intolerance to octreotide in the s.c. formulation and who do not have non treatment related diarrhoea recorded

as an AE after the first dose of octreotide LAR and prior to the start of treatment with lapatinib and capecitabine. A sensitivity analysis of diarrhoea-related primary efficacy endpoint will be conducted using the m-ITT population.

Per Protocol Population

The Per-Protocol (PP) population will comprise all randomised subjects who receive at least one dose of study treatment and who comply closely with the protocol (that is subjects who are not excluded from PP set as per PDMP). The PP population will not be analysed if this population comprises more than 95% or less than 50% of the ITT population. The analysis of primary efficacy endpoint will be repeated using the PP population.

Subjects with potential PDs will be excluded from PP population based on Protocol Deviation Management Plan (PDMP).

Safety Population

The Safety population will comprise all randomised subjects who receive at least one dose of study treatment and will be based on the actual treatment received if this differs from that to which the subject was randomised. This population will be used for the analysis of clinical safety data. Moreover, if a subject who was randomised to Octreotide arm, showed intolerance to octreotide in the s.c. formulation, and took at least one dose of lapatinib or capecitabine, then subject will be included in no Octreotide arm for safety analysis.

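### The graded adverse event table applies its 5% cut-off to both arms pooled, so the grade of uncommon AEs confined to the octreotide arm is not tabulated

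*SAP*

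**What the plan says.** SAP 2.7.2 (Adverse events) describes the table as follows: "A summary of all AEs that occurred in strictly 5% or higher of all the subjects will be provided". No rounding is allowed at the threshold: "event with 4.9% incidence rate should not be included in this table". On layout it says "The summary will be displayed by preferred term (PT) and maximum grade".

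The other general AE outputs in SAP 2.7.2 to 2.7.6 do not mention grade. They are the overview, the tables by system organ class (SOC) and preferred term (PT) with relationship to treatment, the SAE tables, the tables of AEs leading to discontinuation or withdrawal, and the disclosure tables. The AE listing names seriousness, relatedness and action taken, but not grade. SAP 2.7.3 has a maximum-grade rule for the events of special interest (diarrhoea, hepatobiliary, cardiac). SAP 2.7.8 summarises laboratory tests by maximum grade.

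Protocol 9.3.5.2.2 has no frequency limit: "If the AE is listed in the NCI CTCAE (version 4.03) table, the maximum grade will be summarised". SAP section 4, on changes from the protocol analyses, mentions the shorter endpoint list and the diary listing only.

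**The concern.** The effect of octreotide on the safety and tolerability of cancer treatment is a secondary objective that the SAP keeps (Table 1-3). Both arms receive lapatinib and capecitabine, so an AE caused by octreotide tends to sit in one arm. A cut-off on the pooled count then roughly doubles the rate that the arm must reach before the AE is shown with its grade. An AE spread over both arms passes more easily. The filter therefore bears most on the arm-specific events that the comparison is meant to describe. If some of them are Grade 3 or 4, no general table attaches that grade to the event by arm.

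**Working it through.** The documents give no figure of their own to reproduce here. The check is direct counting.

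**Inputs**
- Enrolled: 62. SAP section 1 states that "an interim analysis was performed after 62 patients enrolled using a cut-off date (30-Mar-2016" and, on later recruitment, "Per protocol no further patients were enrolled in the study per IA cut-off".
- Allocation: "Subjects will be randomised in a 1:1 ratio to receive either" (SAP 1.1). Actual arm sizes are not given, so 31 and 31 is an assumption.
- Denominator: "The Safety population will comprise all randomised subjects who receive at least one dose of study treatment" (SAP 2.2). The treated number is not given and is at most 62. SAP 2.2 also moves subjects intolerant of the subcutaneous test dose, if they then take lapatinib or capecitabine, to the no-octreotide arm for safety. The split could therefore be uneven.

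**Smallest count shown.** An AE in k subjects is shown if k/N is at least 5%. For N = 62, 0.05 × 62 = 3.1, so 4 subjects are needed (4/62 = 6.45%). Three are too few (3/62 = 4.84%).

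**Largest one-arm rate left out, with no cases in controls**

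| Safety N | Largest k left out | Pooled rate | Rate in one arm |
|---|---|---|---|
| 62 | 3 | 4.84% | 3/31 = 9.7% |
| 61 | 3 | 4.92% | 3/31 = 9.7% (3/30 = 10.0% if octreotide is the smaller arm) |
| 60 | 2 | 3.33% | 2/30 = 6.7% |

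At N = 60, 3/60 is exactly 5.00% and is shown, hence the step down. With N = 62 and an uneven split, the one-arm rate runs from 3/33 = 9.1% to 3/29 = 10.3%.

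**Under a rule of 5% in either group (31 per arm).** 3/31 = 9.7% and 2/31 = 6.5% are shown. 1/31 = 3.2% is still left out.

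**Which events are exposed.** Protocol 1.3.1 lists AEs seen in 1% to 10% of octreotide patients, among them steatorrhoea and abdominal bloating. One to three cases in 31 (3.2% to 9.7%) fall inside that range. Not every event in the list is at risk: Protocol Table 2 shows dyspepsia in 11% and vomiting in 30% on lapatinib plus capecitabine alone, so those should pass the pooled cut-off from background cases.

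**Constipation.** Protocol Table 2 gives 24/210 (11%) on lapatinib plus capecitabine alone. At that rate 62 × 24/210 = 7.1 cases are expected with no octreotide effect. The binomial probability of 3 or fewer is about 7%. Constipation would probably be shown.

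**The case against.** The strongest reply is that no event disappears. The SOC/PT tables carry every AE by treatment group with no cut-off, so 3 v 0 is visible there, and only its grade is missing. This stands. A reader might infer that the rule removes octreotide harms from the safety report. The documents do not support that.

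The octreotide harms that first come to mind are also largely covered. Gallstones and bradycardia may fall under the hepatobiliary and cardiac groups, which have a maximum-grade rule, though the term list is left to clinical review. Glucose is graded in both directions as a laboratory value. Constipation is common enough on the background regimen that it is neither confined to one arm nor likely to miss the cut-off. One caveat is that Protocol Table 3 (EGF111438) does not list it at 10% or more, so the background rate could be lower. Thyroid events remain exposed, but Protocol 1.3.1 expects them mainly with chronic octreotide treatment.

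Grade 3 or 4 events that are serious, or that lead to discontinuation, also enter tables with no cut-off. Those tables give the event but not its grade.

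Finally, Protocol 9.3.5.2.2 does not prescribe one table of every term, Protocol 9.3.5.2 leaves detail to the analysis plan, and the SAP announces reduced analyses for an abbreviated report. It is therefore too strong to say that the protocol requires the full table. Even so, its wording has no frequency limit, Protocol 9.3.5 asks that deviations from its analysis plan be documented, and SAP section 4 is silent on this one.

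**Conclusion.** The point holds as a minor one. The only general AE table with grade uses a pooled cut-off. It can leave out an AE seen in up to 3 octreotide subjects and no controls, about 9.7% of that arm. That figure assumes roughly 31 per arm and a Safety population of 61 or 62. With 60 treated the figure is about 6.7%. It should not be read as a known rate, because neither the arm sizes nor the treated number is in the documents.

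The loss is limited to the by-arm grade of uncommon AEs that are neither of special interest nor graded through laboratory values: for example steatorrhoea, abdominal bloating, thyroid events or an unexpected AE. Incidence by arm is kept. No primary or secondary diarrhoea result is affected.

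**What to change.** With only 62 subjects, drop the cut-off and show all preferred terms by maximum grade and treatment group. This matches Protocol 9.3.5.2.2 and keeps single Grade 3 or 4 cases. The cost is a longer table.

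At minimum, reword the rule to 5% or higher in either treatment group. That recovers AEs in 2 or 3 of 31, but a severe event in one octreotide subject (3.2%) would still be missing. Any cut-off that is kept should be declared in SAP section 4. Either change is a phrase or two in the SAP and needs no new data.

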2.7.3 Adverse Events of Special Interest

Adverse events of special interest are:

- diarrhoea,
- hepatobiliary events
- cardiac events

A comprehensive list of MedDRA terms based on clinical review will be used to identify each type of event. Changes to the MedDRA dictionary may occur between the start of the study and the time of reporting and/or emerging data from on-going studies may highlight additional adverse events of special interest, therefore the list of terms to be used for each event of interest and the specific events of interest will be based on the SRT agreements in place at the time of reporting.

Summaries of the number and percentage of subjects with these events of special interest will be provided for each type of event separately by SOC and PT.

The worst case approach will be applied at subject level for the event outcome and maximum grade, i.e. a subject will only be counted once as the worst case from all the events experienced by the subject.

In addition, AEs of special interest will be listed separately.

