Study completion will be at the end of 24 weeks treatment with lapatinib and capecitabine, or disease progression, unacceptable toxicity or subject withdrawal if this is sooner. SAEs and other safety data will be reported beyond 24 weeks in subjects who continue treatment with lapatinib and capecitabine until disease progression in countries where the Sponsor is supplying lapatinib and capecitabine. SAEs will be followed up until resolution or stabilization of the event or until the subject is lost to follow-up.

The efficacy of prophylactic octreotide in reducing the frequency and severity of diarrhoea is the primary endpoint of this study. Each episode of diarrhoea will be recorded by the investigator as an AE in the eCRF in accordance with the standard AE reporting procedure. Actions associated with the management of diarrhoea (use of anti-diarrhoeal medication, unscheduled visits to healthcare professionals, treatment interruption, rehydration) will be recorded in the eCRF.

Subjects will complete the DMD and the FACIT-D to provide an additional perspective on the effects of treatment-associated diarrhoea.

Diarrhoea, nausea and vomiting, dermatological events, hepatobiliary, cardiovascular and respiratory events have been identified as events of special interest relating to lapatinib. Hand and foot syndrome has been identified as an event of special interest relating to capecitabine. There are no events of special interest relating to octreotide.

The schedule of all assessments is presented in [Table 1-1](#) for subjects who receive octreotide and [Table 1-2](#) for subjects who do not receive octreotide.

Table 1-1 Time and events schedule; Subjects who receive octreotide.

	Screen ¹	Octreotide Dose 1	Lapatinib and Capecitabine Cycle ^{9,10}			Withdrawal from Study Treatment or End of Study ¹⁴
			Cycle 1	Cycle 2 (Octreotide Dose 2)	Cycles 3 to 8	
Procedures						
Informed Consent	X					
Inclusion/Exclusion Criteria	x ²	x ²				
Demographics	X					
Breast Cancer Medical/Surgical and Treatment History	X					
Efficacy and Safety Assessments						

AE/Toxicity Assessment		x	x	x	x	x ¹⁵
Disease Assessment	x ³	(x) ⁵	(x) ⁵	(x) ⁵	(x) ⁵	x
PROs ⁶		x ⁷	x ¹¹	x	x	x
Concurrent Medications	X	x	x	x	x	x
Physical Exam	X					x
Weight, Height, Vital Signs (Temp, BP, pulse)	X					x
ECOG Performance Status	x ⁴					x
Cardiac function	X					x ¹⁶
ECG	X					(x) ¹⁷
Lab Assessments						
Liver function	X	(x) ⁵	(x) ⁵	(x) ⁵	(x) ⁵	x
Pregnancy Test	X					x
Study Treatments						

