3.3 Sample Size Re-estimation

Sample size re-estimation is not planned for this study.

4 Change to protocol specified analyses

Since final CSR will be an abbreviated CSR, not all endpoints will be analysed. [Table 1-3](#) contains reduced list of endpoints as compared to protocol.

Secondary endpoint Patient reported Diarrhoea Management Diary (DMD) is reported using a listing of patients reporting changes in bowel movements from baseline (frequency and/or consistency), recorded in the DMD.

5 Appendix

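### The SAP cuts the adverse events of special interest from seven to three without itemising the change; the main loss is a grouped, worst-grade count by arm for rash and pneumonitis

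*SAP*

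**What the plan says.** Protocol 9.3.5.2.2 plans a dedicated safety summary. It names the content by example, "Characteristics (e.g. number of occurrences, action taken, grade and severity", and then the events: "diarrhoea, rash, nausea, vomiting, hepatobiliary events, cardiac events, and pneumonitis". That is seven groups.

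SAP 2.7.3, under "Adverse events of special interest are", lists three: diarrhoea, hepatobiliary events and cardiac events. Each is to be identified from a MedDRA term list agreed on clinical review, with each subject counted once at the worst outcome and maximum grade. The display is described as "Summaries of the number and percentage of subjects with these events of special interest will be provided for each type of event separately by SOC", with a further breakdown into preferred terms. The section adds that terms and events will follow Safety Review Team (SRT) agreements in force when the report is written.

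SAP 1.1 carries the wider list over from Protocol 3.1: "Diarrhoea, nausea and vomiting, dermatological events, hepatobiliary, cardiovascular and respiratory events have been identified as events of special interest relating to lapatinib". It adds: "Hand and foot syndrome has been identified as an event of special interest relating to capecitabine".

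SAP section 4, on changes from the protocol, says "Since final CSR will be an abbreviated CSR, not all endpoints will be analysed". It points to the shortened Table 1-3 and to the diary listing, and does not mention events of special interest. Table 1-3 keeps the safety and tolerability objective.

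**The concern.** The SAP disagrees with the protocol on which events get a dedicated summary, and with itself, because 1.1 and 2.7.3 give different lists. Section 4 is where a reader would look for the explanation, and it has none.

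The special-interest table differs from the general adverse event tables in SAP 2.7.2. It pools a reviewed set of terms and counts a subject once at worst grade across that set; the general tables work preferred term by preferred term. The difference matters for a toxicity that can be coded to more than one term or that is rare.

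Two of the dropped groups have a stated role in the protocol. Section 5.12.1.1 gives finding the incidence of dermatological events as one purpose of skin monitoring. Section 7.1.9 groups the protocol-specific SAEs as cardiac, hepatic and pneumonitis; SAP 2.7.3 keeps the first two and drops the third without a reason. Nausea and vomiting are recognised effects of octreotide as well (Protocol 1.3.1), so they bear on the safety objective that was kept.

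**Working it through.** The plan gives no figure to reproduce. The check compares the lists and then asks what the remaining tables would show.

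**1. The lists**

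| Event group | Protocol 9.3.5.2.2 | SAP 1.1 | SAP 2.7.3 |
|---|---|---|---|
| Diarrhoea | yes | yes | yes |
| Hepatobiliary | yes | yes | yes |
| Cardiac | yes | yes (cardiovascular) | yes |
| Rash | yes | yes (dermatological) | no |
| Nausea | yes | yes | no |
| Vomiting | yes | yes | no |
| Pneumonitis | yes | yes (respiratory) | no |
| Hand-foot syndrome | no | yes | no |

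Seven minus three leaves four dropped: rash, nausea, vomiting and pneumonitis.

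**2. Where the four would still appear.** SAP 2.7.2 gives all-AE, related-AE and SAE tables by SOC and PT, with a subject counted once in each SOC row. It also gives a preferred-term table by maximum grade for events in at least 5% of all subjects, and a listing that includes action taken. SAP 2.7.5 adds discontinuation and withdrawal tables. Protocol 7.4.2 makes Grade 3 pneumonitis an SAE, so it enters the SAE tables.

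**3. The 5% threshold.** The SAP introduction gives 62 enrolled. 3/62 = 4.84% falls short and 4/62 = 6.45% qualifies, so 4 subjects are needed. This takes 62 as the denominator; if the safety population were 60, then 3/60 = 5.00% would just qualify.

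**4. Common events.** Background rates are from Protocol Table 2 (EGF100151, N = 210), where each event is one preferred-term row:

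- nausea 98/210 = 47%; expected 0.47 × 62 = 29.1
- vomiting 63/210 = 30%; expected 0.30 × 62 = 18.6
- rash 61/210 = 29%; expected 0.29 × 62 = 18.0

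All are far above 4. At these rates, coded to one term, each reaches the maximum-grade table with probability near 1.

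**5. Rare events.** The documents give no pneumonitis rate, so the rates here are assumptions. With X binomial(62, p), P(X ≥ 4) = 1 − Σ C(62,k) p^k (1−p)^(62−k), k = 0 to 3:

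| Assumed true rate | Expected of 62 | P(reaches table) |
|---|---|---|
| 1% | 0.6 | 0.4% |
| 2% | 1.2 | 3.6% |
| 3% | 1.9 | 11.6% |
| 5% | 3.1 | 37.6% |

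This assumes every case is coded to one term; splitting lowers each term's chance.

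**6. Splitting (illustration only).** A toxicity with a true rate of 10% under one term reaches the table with probability 88%. Spread equally over three terms (3.33% each), each term does so with probability 15%.

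**The case against.** The strongest reply is that little is lost. Nausea and vomiting are single terms in Protocol Table 2, so a grouped table would largely repeat rows already planned. Rash is also one row there, at 29%, so that source gives no support for a split. SOC rows give a subject-level count by arm for each body system, and severe pneumonitis appears among the SAEs. The SAP says openly that the report is abbreviated after futility, and its section 5.1 provides for a team review of which analyses remain appropriate after termination. Both arms receive lapatinib and capecitabine, and both documents state that octreotide has no events of special interest.

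Most of this stands and sets the size of the point. A reader might infer that the four events will be reported only as scattered preferred terms, or that no subject-level incidence of skin or lung toxicity by arm will exist. The documents do not support either reading, for the reasons just given. Protocol Table 13 does grade maculo-papular and acneiform rash separately, which makes splitting possible, but how far it happens here is an assumption. Nor is hand-foot syndrome a broken commitment: Protocol 9.3.5.2.2 does not list it.

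Three parts of the reply fall short. A SOC row is neither graded nor confined to a reviewed set of rash or lung terms. The general abbreviated-report wording does not itemise this cut. The SRT clause could change the list, but as written it restores none of the four.

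**Conclusion.** The point holds as a modest reporting gap that should be corrected. The SAP reduces a protocol-specified list from seven to three, contradicts its own section 1.1, and does not itemise the change in section 4. The material consequence is confined to rash/dermatological and pneumonitis/respiratory events, for which no planned table gives a grouped count by arm with each subject once at worst grade. For a rare lung event the maximum-grade table is unlikely to help: under assumed true rates of 1% to 3%, the chance of reaching it is 0.4% to 11.6% with 62 subjects. For nausea and vomiting the loss is smaller: the dedicated summary of occurrences and action taken, which the protocol offers only as examples and which the SAP does not specify even for the three events it keeps.

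The conclusion rests on 62 as the denominator and on reading the SAP 2.7.3 list as it stands. It claims no effect on the primary analysis or the futility decision.

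**What to change.** In SAP 2.7.3, restore rash/dermatological events and pneumonitis/respiratory events, and add nausea and vomiting back so that the list agrees with Protocol 9.3.5.2.2. Fix the MedDRA term list for each by clinical review before the tables are run, and use the subject-level worst-grade table by arm already planned for the three retained events. Adding hand-foot syndrome is optional; if it stays out, align SAP 1.1 with 2.7.3. Should the sponsor prefer to keep the shorter list, the minimum is an entry in SAP section 4 that names the dropped events and gives the reason, with SAP 1.1 brought into line.

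The cost is a few more runs of an existing table program and the added term lists. The change concerns reporting only: no new data are needed and no clinical rule is touched.
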